 1% BSA is approximately equal to the surface area of the subject's palm and fingers, with the fingers extended yet grouped together, creating a flat oval-like surface area.

	

5. Subject has an Investigator's Global Assessment (IGA) score of at least three (3 = moderate) at the Baseline Visit.

6. Subject is in good general health and free of any disease state or physical condition that might impair evaluation of IV or which, in the investigator's opinion, exposes the subject to an unacceptable risk by study participation.

7. Females must be post-menopausal, surgically sterile, or use an effective method of birth control. Women of childbearing potential (WOCBP) must have a negative urine pregnancy test (UPT) at the Baseline Visit.

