Study Endpoints	
Efficacy Endpoint(s): IGA scores and the clinical signs and symptoms of IV will be dichotomized to "treatment success" or "treatment failure" where "treatment success" is defined as at least a two grade decrease in severity score relative to Baseline. Dichotomization of scores for clinical signs and symptoms of IV will exclude subjects with Baseline scores of 0 or 1 unless the corresponding sign score at follow-up visits is >1.
 
The primary efficacy endpoint will be the proportion of subjects with IGA "treatment success" at EOS, where EOS is the subjects last completed post-Baseline visit.
 
Secondary efficacy endpoints (observed data only) include:
 

• The proportion of subjects with IGA "treatment success" at Days 15 and 29.

• The proportion of subjects with a IGA score of 0 or 1 representing "cleared" or "almost cleared" at EOS.

• The proportion of subjects rated "treatment success" for each of the clinical signs and symptoms of IV at Days 15, 29, and EOS.

• Changes in percent BSA with IV in the Treatment Area at Days 15, 29, and EOS relative to Baseline.

• Change from Baseline in 5-D pruritus score at Days 15, 29, and EOS.

• Changes in [REDACTED] at Days 15, 29, and EOS relative to Baseline.

	
Safety Endpoint(s):          Safety endpoints will include assessment of UPT (as applicable), clinical laboratory testing, and AEs, including serious adverse events (SAEs).

Sample Size Calculations
	
No formal power calculations were conducted to establish sample size. The sample size was selected empirically to enable sample size calculations for future pivotal studies.

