
Statistical Methods
	
All statistical analyses and summaries will be prepared using SAS® unless otherwise stated. All subjects enrolled in the study who were dispensed and applied test article at least once will be included in the analysis of safety and will be considered the Safety population. All randomized subjects who were dispensed the test article will be considered the intent-to-treat (ITT) population. The per-protocol (PP) population will be a subset of the ITT population consisting of subjects who have completed the study without significant protocol deviations. The statistical analysis plan will provide details regarding inclusion in the PP population. Missing values for the IGA score at EOS in the ITT population will correspond to IGA “treatment failure”. All other analyses for both ITT and PP populations will use observed data only. Efficacy analyses will be performed on both the ITT and PP populations with the ITT population considered primary.
 
Demographic and baseline characteristics will be summarized by treatment group for the Safety, ITT, and PP populations. Frequency counts and percentages will be reported for categorical data and sample size, mean, median, standard deviation (SD), minimum and maximum will be reported for the continuous variables.
 
Efficacy Analyses:          For each of the efficacy endpoints (IGA and signs of IV), the following summaries will be prepared at Days 15, 29, and EOS:
 
 
• Frequency distribution of observed scores
 
• Frequency distribution of change from Baseline
 
• Shift tables for changes from Baseline to Visits 2, 3, and 4
 
• Frequency distribution of treatment success rates
 
 
At EOS, 95% confidence intervals will be calculated for the difference in proportions between treatment groups for rates of treatment success. The treatment groups will be compared with respect to “treatment success” rates for IGA and each sign of IV using Fisher’s Exact Test. The proportion of subjects with an IGA score of 0 or 1 will be analyzed likewise using Fisher’s Exact Test.
 
Descriptive statistics (including mean, median, SD, minimum, and maximum) for observed and change from Baseline values in the percent BSA affected in the Treatment Area at each visit will be presented.
 
For 5-D pruritus score and [REDACTED], descriptive statistics for observed and change from baseline values will be provided by treatment group at Baseline and at Days 15, 29, and EOS. The treatment groups will be compared with respect to the change from Baseline using mixed model of repeated measures (MMRM) including terms for treatment, visit, treatment by visit interaction, and the Baseline value serving as the covariate.

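### The primary Fisher's exact test is valid but conservative at 44 per arm; an uncorrected CMH test stratified by Baseline IGA would be a cheap, modest gain in power

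*Combined protocol and SAP*

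**What the plan says.** All references are to the Protocol Synopsis.

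- **Primary endpoint (Study Endpoints).** IGA success at EOS, meaning "at least a two grade decrease in severity score relative to Baseline".
- **Test (Statistical Methods, Efficacy Analyses).** The arms are compared on success "rates for IGA and each sign of IV using Fisher’s Exact Test". For the secondary endpoint of clear or almost clear: "The proportion of subjects with an IGA score of 0 or 1 will be analyzed likewise using Fisher’s Exact Test".
- **Interval (same section).** At EOS, "95% confidence intervals will be calculated for the difference in proportions between treatment groups for rates of treatment success". No interval method is named, and no alpha or sidedness is given for the test.
- **Entry (Inclusion Criterion 5).** An IGA "score of at least three (3 = moderate) at the Baseline Visit". The scale stops at 4, so Baseline IGA is 3 or 4 for everyone.
- **Missing data (Statistical Methods).** "Missing values for the IGA score at EOS in the ITT population will correspond to IGA" failure, so the primary analysis keeps every ITT subject. The secondary endpoints, including IGA 0/1, use observed data only.
- **Sample size.** About 88 subjects, 44 per arm. "No formal power calculations were conducted to establish sample size"; the number was chosen to inform pivotal planning.
- **Baseline adjustment.** The repeated-measures model for 5-D pruritus has treatment, visit and their interaction, "and the Baseline value serving as the covariate". Nothing similar is stated for IGA.

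**The concern.** Two features of the planned test cost power.

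First, Fisher's test conditions on the total number of successes. With 44 per arm, the attainable p-values are coarse enough that the true false-positive rate is well below the nominal level.

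Second, the test pools two Baseline groups that face different targets. A subject at IGA 3 must reach 1 or less to count as a success; a subject at IGA 4 must reach 2 or less. For IGA 0/1 the target is fixed, so the required drop differs instead: two grades from 3, three from 4. If Baseline IGA predicts success, pooling discards information that is already collected on every subject.

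At stake are the power of the one formal primary comparison and its agreement with the interval reported beside it. With the interval method left open, a report could show p above 0.05 next to a 95% interval that excludes zero.

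**Working it through.** The plan gives no power or effect size, so there is no figure of its own to reproduce.

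**Inputs from the documents:** 44 per arm, 1:1, no stratification factor stated, Baseline IGA 3 or 4, missing EOS IGA counted as failure. **Assumed:** two-sided 5% (in line with the 95% interval), all success rates, and the share of subjects at IGA 4 ('severe' below).

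**1. True size of Fisher's test.** Enumerate all 45 × 45 outcomes:

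size(p) = Σₐ Σ_b Bin(a; 44, p) · Bin(b; 44, p) · 1{Fisher p(a,b) ≤ 0.05}

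| Common success rate | 5% | 10% | 20% | 35% | 50% |
|---|---|---|---|---|---|
| True size | 0.5% | 1.9% | 2.5% | 3.1% | 2.6% |

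The maximum is 3.06%. The same enumeration gives a maximum of 6.0% for the unstratified Pearson chi-square and 4.8% for Boschloo's exact test.

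**2. CMH statistic, without continuity correction.** For stratum k (Baseline IGA 3, 4) with a_k active successes, n₁k active and n₀k vehicle subjects, m_k successes in all and N_k subjects:

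X² = [Σ(a_k − n₁k·m_k/N_k)]² / Σ[n₁k·n₀k·m_k·(N_k − m_k) / (N_k²(N_k − 1))], compared with 3.84.

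Its simulated size is 4.1-5.1% over 36 null settings with rates of 5-50% and 5-50% severe. It is lower for rarer success: about 2.1% at a rate of 3% and 0.9% at 2%.

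**3. Power** (%; 200,000 simulated trials per row, Baseline IGA falling at random in each arm; a/b means the rates at IGA 3/IGA 4, vehicle vs active):

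| Assumed rates | Fisher | Pearson | Boschloo | CMH | CMH − Fisher | CMH − Pearson | CMH − Boschloo |
|---|---|---|---|---|---|---|---|
| 5 vs 20 | 46.7 | 61.7 | 54.0 | 58.6 | +11.9 | −3.1 | +4.6 |
| 10 vs 30 | 56.1 | 68.3 | 65.0 | 66.5 | +10.4 | −1.8 | +1.5 |
| 25 vs 50 | 61.2 | 70.1 | 67.4 | 68.3 | +7.1 | −1.8 | +0.9 |
| 20 vs 45 | 64.3 | 73.2 | 71.5 | 71.6 | +7.3 | −1.6 | +0.1 |
| 30 vs 60 | 74.3 | 81.3 | 80.2 | 81.1 | +6.8 | −0.2 | +0.9 |
| 35% severe, 35/10 vs 65/30 | 65.3 | 73.8 | 71.3 | 76.8 | +11.5 | +3.0 | +5.5 |
| 35% severe, 15/40 vs 40/70 | 67.9 | 76.2 | 73.8 | 78.0 | +10.1 | +1.8 | +4.2 |
| 50% severe, 15/45 vs 40/75 | 66.1 | 74.4 | 72.8 | 79.8 | +13.7 | +5.4 | +7.0 |
| 20 vs 50 | 80.5 | 86.5 | 85.0 | 85.2 | +4.7 | −1.3 | +0.2 |
| 35% severe, 12/35 vs 42/65 | 80.3 | 86.3 | 84.9 | 87.3 | +7.0 | +1.0 | +2.4 |
| 20 vs 60 | 96.3 | 97.9 | 97.5 | 97.6 | +1.3 | −0.3 | +0.1 |

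Rows with one rate per arm assume that Baseline IGA is not prognostic.

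**4. Wider grid.** Vehicle success 5-30%, active 15-45 points higher, 20-50% severe, common treatment odds ratio. CMH minus Fisher:

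| Fisher power | Odds ratio of Baseline IGA for success 1/3 to 3 | Largest gain, odds ratio ≤1/5 or ≥5 |
|---|---|---|
| 47-74% | +7.1 to +12.2 | +19.0 |
| 78-83% | +4.8 to +6.9 | +11.4 |
| above 96% | +0.1 to +1.9 | +2.9 |

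One strongly prognostic case outside the grid (35% severe, 5/45 vs 25/75) gives Fisher 59.2, CMH 78.8: +19.6.

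**5. Agreement of test and interval.** Take 20/44 vs 11/44, a difference of 9/44 = 20.5 points. Fisher p = 0.073. The Wilson limits are 31.7 to 59.9 and 14.6 to 39.4, so the Newcombe lower limit is 20.5 − √((45.5 − 31.7)² + (39.4 − 25.0)²) ≈ 0.5 and the upper limit is 38.3. The interval excludes zero although p exceeds 0.05. By enumeration, where Fisher's power is 47-74% this happens in 9.1-15.0% of trials with a Wald interval and 6.2-11.0% with Newcombe. CMH with the Mantel-Haenszel interval (Sato variance) disagrees in 1.5-2.5%.

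**The case against.** **No error and no missed target.** Fisher's test is valid, and an exact test is a legitimate choice in an 88-subject Phase 2 trial. The visible text sets no power target and no decision rule on this p-value. This stands, and it limits the weight of the point. It does not remove it, because the synopsis does plan a formal comparison.

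**Stratification is not the main cause.** A reader might infer that adding Baseline IGA is what yields the 7-14 points. The figures do not support that. In the 47-74% band, moving from Fisher to Pearson alone gives +7.0 to +15.0, and in all five non-prognostic rows there CMH is slightly below Pearson. Pearson is not a like-for-like benchmark, however, since its size reaches 6.0%.

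**Boschloo's test recovers much of the gain and stays exact.** This stands in part. CMH's advantage is about 0 to 5 points when Baseline IGA is not or only weakly prognostic, or when few subjects are at IGA 4. It is 7 points or more only when prognosis is clear. Even a prognostic Baseline does not ensure a large margin: for IGA 0/1 at 35% severe, 25/10 vs 55/30 and a full 44 per arm, Fisher, Boschloo and CMH give 69.7, 76.2 and 78.1, so CMH leads Boschloo by only 1.9.

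**Baseline is already used.** Success is a change from Baseline, so it enters the endpoint. True; what is absent is stratification of the test. The pruritus covariate shows that adjustment is familiar to the plan, but not that the plan contradicts itself.

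**Details may sit elsewhere.** The available text is the synopsis and schedule. The interval method and alpha may be settled in fuller text, in which case that part falls away. An unstated interval method would not carry this point alone.

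**Conclusion.** The point holds as an efficiency improvement of low priority. That Fisher's true size is at most 3.1% follows from 44 per arm and the assumed nominal 5%. The power gains rest on assumed success rates and severity mixes: roughly 7-14 points where Fisher's power is 47-74%, 5-7 near 80% and about 1 above 96%, rising to about 19-20, 11 and 3 if Baseline IGA is strongly prognostic. These are ranges over the scenarios examined, not general bounds. Relative to Pearson, stratification itself adds about −3 to +5 points unless prognosis is strong.

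Two stronger readings are not supported. One is that the primary analysis is wrong or the trial underpowered: the test controls type I error, and the plan sets no power target to fall short of. The other is that pivotal planning would be distorted: the arm proportions are the same whichever test is used. What changes is the primary p-value, its agreement with the interval, and, if Baseline IGA is prognostic, the interval's width (SD of the difference 10.2 points crude against 9.6 Mantel-Haenszel at best; 10.0 for both if not prognostic).

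**What to change.** Before unblinding, pre-specify in the protocol and SAP, for IGA success at EOS:

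- a CMH test stratified by Baseline IGA (3 vs 4), two-sided 5%, explicitly without continuity correction (with it, power at 10 vs 30% is 55.3%, against 56.1% for Fisher);
- the matching Mantel-Haenszel risk difference with a 95% interval (Sato variance);
- Fisher's exact test as a sensitivity analysis.

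Apply the same to IGA 0/1 at EOS, noting that it uses observed data only, so the number analysed may be below 44 per arm. If the sponsor prefers an exact type I guarantee, name Boschloo's test instead. In either case, state the interval method and alpha.

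**Cost.** A short text change and no new data, since entry requires a Baseline IGA. The exact guarantee is lost with CMH (simulated size about 4-5% at null rates of 5% or more; interval coverage 94.1-95.4%). Up to about 3 points of power are lost against an unstratified chi-square if Baseline IGA is not prognostic.

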## PROTOCOL SYNOPSIS

Title	A Randomized, Double-Blind, Vehicle-Controlled Study To Evaluate The Safety And Efficacy Of 146-9251 Cream Applied Twice-Daily For Six Weeks In Subjects With Ichthyosis Vulgaris
Study Type	Phase 2
Test Articles	1. 146-9251 Cream (Crown Laboratories) 2. Vehicle Cream
Study Objective	The objective of this study is to determine and compare the safety and efficacy of topical 146-9251 Cream and vehicle cream applied twice daily for up to 6 weeks in subjects with moderate to severe ichthyosis vulgaris (IV).
Study Design	Double-blind, randomized, multicenter, vehicle-controlled study.
Treatment Groups	Eligible subjects will be randomized (1:1) to one of two treatment groups: 1. 146-9251 Cream 2. Vehicle cream The assigned test article will be applied by the subjects twice daily for up to 6 weeks.
Duration of Treatment	Up to 6 weeks
Duration of Study	Up to 6 weeks for an individual subject
Study Population	Male or female subjects at least 12 years of age with moderate to severe IV.
Total Number of Subjects	Approximately 88 subjects will be enrolled (44 per treatment arm).
Number of Sites	Approximately 5 sites will participate in the study.
Inclusion Criteria	To enter the study, a subject must meet the following criteria:  1. Subject is a male or female and is at least 12 years of age at the time of enrollment. 2. Subject has provided written informed consent/assent. A subject under 18 years of age must provide written informed assent and be accompanied by the parent or legal guardian at the time of assent/consent signing. The parent or legal guardian must provide informed consent for the subject. If a subject becomes 18 years of age during the study, the subject must provide written informed consent at that time to continue study participation. 3. Subject and parent/guardian (if applicable) are willing and able to apply the test article(s) as directed, comply with study instructions, and commit to all follow-up visits for the duration of the study. 4. Subject has a clinical diagnosis of IV involving a minimum of 5% body surface area (BSA) within the Treatment Area.  The Treatment Area is defined as the entire body exclusive of the a) head and neck and b) mucosal areas.

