	
1. Visit 1 (Day 1) - Screening/Baseline Visit: At Visit 1, study staff will explain the study procedures and an informed consent/assent must be signed prior to the initiation of any study-related procedures. At this visit, consenting/assenting subjects will have their medical history and demographics, concomitant medications and procedures/therapies, and inclusion/exclusion (I/E) criteria reviewed to determine subject eligibility. Subjects that require a “washout” period prior to enrollment into the treatment phase to meet I/E criteria requirements will be required to return to the clinic within 45 days to complete the remaining activities. Subjects who require “washout” for longer than 45 days will be re-consented. All WOCBP must have a negative UPT. A brief physical exam, vital signs (including height, and weight), clinical laboratory testing, photography, which is optional, at select site(s) per a photo guide provided by the Sponsor, and clinical evaluations will be performed prior to test article application. The Treatment Area will be defined as the entire body exclusive of a) the head and neck and b) mucosal areas*. The location of the IV to be treated and the percent BSA with IV in the Treatment Area will be recorded prior to test article application. Subjects who meet all inclusion criteria and no exclusion criteria will be randomized and assigned to the next available (lowest) subject number in ascending order. The test article will be weighed prior to dispensing to subjects. Test article, Subject Instruction Sheet, and Subject Diary with completion instructions will be dispensed. At this visit, study personnel will review the Subject Instruction Sheet and the subject and parent/guardian (if applicable) will be instructed on how and where to dispense and apply test article to all affected skin in the Treatment Area and to record applications in the Subject Diary. Subjects will apply the first dose of the assigned test article to all affected skin in the Treatment Area under staff supervision. Any adverse events (AEs) post-application will be recorded. Subjects will apply the assigned test article to all affected skin in the Treatment Area twice daily for up to 6 weeks. The subject will then be scheduled for Visit 2.
 
* Note disease on the neck and face if present may be treated with a bland moisturizer, but shall not be evaluated.
 
2. Visit 2 (Week 2, Day 15 ± 2) and Visit 3 (Week 4, Day 29 ± 2): Subjects enrolled into the study will return to the clinic at Weeks 2 and 4 for the study staff to perform the clinical evaluations, record percent BSA with IV in the Treatment Area, collect, review and dispense a new Subject Diary for test article compliance, update concomitant medications and procedures/therapies, record AEs, collect and weigh used test article and dispense test article if necessary. Photography, which is optional, will be performed at select site(s) per a photo guide provided by the Sponsor. Subjects whose IV is completely clear (IGA score = 0 and all clinical signs of IV = 0 [scaling = 0, fissuring = 0, and erythema = 0]) at Day 15 or Day 29 will complete the end of study (EOS) procedures. These subjects will have completed the study. Subjects whose IV is NOT completely clear will be instructed to continue twice daily treatment until the next visit and to record all applications in the Subject Diary. The subject will be scheduled for the next visit.
 
3. Visit 4 (Week 6, Day 43 ± 3 [OR Day 15 ± 2 or Day 29 ± 2 for subjects who are clear]) – End of Treatment/End of Study or Early Discontinuation: These activities may occur as scheduled at the end of the 43-day treatment period or earlier if (a) the subject is to be dropped from the study or (b) the subject’s IV within the Treatment Area is completely clear at Day 15 or Day 29. At this visit, the study staff will perform the clinical evaluations, record percent BSA

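### The repeated-measures model for 5-D pruritus holds the Baseline slope equal at all visits; a Baseline-by-visit term is a nearly free improvement whose gain depends on undocumented correlations

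*Combined protocol and SAP*

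**What the plan says.** The Statistical Methods row of the Protocol Synopsis (Efficacy Analyses) compares the arms on change from Baseline in 5-D pruritus, and in a redacted measure, by an MMRM "including terms for treatment, visit, treatment by visit interaction, and the Baseline value serving as the covariate". No Baseline-by-visit term appears there or elsewhere in the document, and the covariance structure is not stated.

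The secondary endpoint in the Study Endpoints row is "Change from Baseline in 5-D pruritus score at Days 15, 29, and EOS". In the same row, EOS is defined in the sentence on the primary endpoint: "where EOS is the subjects last completed post-Baseline visit".

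Under Study Procedures, subjects whose disease is completely clear "at Day 15 or Day 29 will complete the end of study (EOS) procedures", and "These subjects will have completed the study". On missing data, apart from the IGA score at EOS, the plan says: "All other analyses for both ITT and PP populations will use observed data only".

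**The concern.** A programmer who follows the listed terms fits one Baseline slope for Day 15, Day 29 and the final visit. Each pruritus score looks back two weeks. The Baseline window ends at first dosing, so the Day 15 window adjoins it, while the Day 43 window starts four weeks later and under treatment. It is reasonable to expect Baseline to predict the first score better than the last. A common slope then leans towards the early visits and over-adjusts the final one.

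Two things could follow: a noisier final-visit contrast and, if subjects who clear early have no final-visit record, a shifted one. The trial's size was chosen so that its results could feed sample size calculations for pivotal studies. An inflated residual variance at the final visit could therefore carry into later planning.

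**Working it through.** **Inputs.** From the document: 44 subjects per arm, 1:1 allocation, three post-Baseline time points. The sample size was set empirically, so there is no stated power, effect size or SD to reproduce. All correlations, SDs, effects and clearing rates below are assumptions.

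**Formula, complete data.** Let β_v be the slope of the visit-v score on Baseline B, and Σ the residual covariance, with diagonal elements σ_v². Analysing change subtracts 1 from every slope and leaves their differences alone. The common slope estimated by generalised least squares is

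b* = (1'Σ⁻¹β) / (1'Σ⁻¹1),

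and the variance of the visit-v treatment contrast is multiplied by

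1 + (β_v − b*)² var(B) / σ_v².

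Randomisation balances Baseline in expectation, so the contrast stays unbiased whatever b* is.

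**One case in full.** Take unit SDs, Baseline correlations 0.8/0.6/0.4 and residual correlation 0.6.
- Residual variances are 1 − ρ² = 0.36, 0.64 and 0.84.
- The visit weights in b* are 0.831, 0.171 and −0.002, so b* = 0.831×0.8 + 0.171×0.6 − 0.002×0.4 = 0.767.
- The final-visit multiplier is 1 + (0.767 − 0.4)²/0.84 = 1.16.

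**All cases, unit SDs:**

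| Baseline correlations (Day 15/Day 29/final) | Residual correlation | b* | Final-visit variance multiplier |
|---|---|---|---|
| 0.6/0.6/0.6 | any | 0.600 | 1.00 |
| 0.7/0.6/0.5 | 0.4 | 0.626 | 1.02 |
| 0.7/0.6/0.5 | 0.6 | 0.641 | 1.03 |
| 0.8/0.65/0.5 | 0.4 | 0.722 | 1.07 |
| 0.8/0.65/0.5 | 0.6 | 0.761 | 1.09 |
| 0.8/0.6/0.4 | 0.4 | 0.710 | 1.11 |
| 0.8/0.6/0.4 | 0.6 | 0.767 | 1.16 |

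**Sensitivity to SD.** The slope is the correlation times the SD ratio, so falling correlations need not mean falling slopes. With SDs rising as 1/1.15/1.3, the slopes for 0.8/0.6/0.4 become 0.80, 0.69 and 0.52. At residual correlation 0.6, b* is 0.818 and the multiplier is 1 + (0.818 − 0.52)²/1.42 = 1.06. For 0.8/0.65/0.5 (residual correlation 0.4) the excess falls to 1.4%, and for 0.7/0.6/0.5 to 0.2%. A falling SD works the other way (simulation below).

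**Simulation, complete data.** An unstructured-covariance MMRM was fitted with one slope and with visit-specific slopes, assuming an SD of 4 points and true effects of −1, −1.5 and −2. Final-visit SEs at 44 per arm:
- Correlations 0.5/0.5/0.5: 0.737 for both models.
- 0.7/0.55/0.4: 0.802 against 0.781 (ratio 1.027; variance ratio 1.027² = 1.05).
- 0.7/0.55/0.4 with SDs 4/3.5/3: 0.610 against 0.588 (ratio 1.037).
- 0.8/0.5/0.2, an extreme fall: 0.994 against 0.833 (ratio 1.19).

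**Simulation, early exit.** Correlations were 0.7/0.55/0.4 and the true final effect −2.00. Clearing depended on observed pruritus, Baseline or change.

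| Third visit | Clearing at Day 15/Day 29, active v vehicle | One slope | Visit-specific slopes |
|---|---|---|---|
| Day 43, cleared subjects missing | 10%/15% v 2%/3% | −1.92 to −2.23 | −1.98 to −2.05 across both clearing rates |
| Day 43, cleared subjects missing | 20%/25% v 3%/5% | −1.79 to −2.40 | (as above) |
| Last completed visit (example) | 10%/15% v 2%/3% | −2.157 (SE 0.805) | −2.161 (SE 0.791) |

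On the Day 43 reading, flat slopes gave no shift, and the extreme fall gave up to about −0.9 points. On the last-completed-visit reading, the two models agreed within about 0.015 points in every case run, including the extreme one.

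**The case against.** The strongest reply is that the text is a synopsis and its list of terms is introduced by a word that does not exclude others. That is fair, but nothing else in the document supplies the term, so the literal reading is the one likely to be programmed.

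Second, the document gives no correlation, SD or slope. This stands: the precision loss is conditional, and it is zero if slopes are equal. How the redacted measure behaves is unknown. A reader might take the steepest case (18% extra variance in one simulation of 0.8/0.6/0.4) and conclude that the plan wastes 88 × (1 − 1/1.18) ≈ 13 subjects. The document does not support that as an expected loss. The closed form gives 11 to 16% for those correlations, and milder decay gives much less.

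Third, a reader might infer that early exit of cleared subjects biases the final-visit effect. As a flat statement this is not supported. The endpoint is worded at EOS, and the Visit 4 description allows that visit to fall at Day 15 or Day 29 for clear subjects. On that reading they have a final value and nothing is extrapolated. The EOS definition is, however, attached to the primary endpoint, so the Day 43 reading remains open. Even then the direction depends on what drives clearing. The exit rule uses IGA and clinical signs, not pruritus, so the simulated mechanisms are only stand-ins.

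Fourth, the stakes are limited: these are secondary endpoints with no power target, and the primary IGA comparison uses Fisher's exact test. This stands and sets the grade of the point.

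**Conclusion.** The point holds as a minor, nearly free improvement. The listed model constrains the Baseline slope to be equal at all visits. If the Baseline relationship weakens over time, the final-visit variance is inflated by about 2 to 7% under moderate decay (9% for 0.8/0.65/0.5 if the residual correlation is 0.6) and 11 to 16% under steep decay. Those figures assume constant SDs. If SD rises over the visits, the decaying cases fall to about 0 to 6%; if it falls, the penalty grows somewhat. Only a near-collapse of the Baseline correlation, to 0.2, produced a large loss.

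There is no bias with complete data. A shift of about −0.4 to +0.2 points on a true −2 arose in the moderate case only where the third visit was Day 43, cleared subjects were missing there, and clearing was frequent and unequal by arm. With EOS as the last completed visit, the slope restriction causes essentially no shift. That version of EOS mixes Day 15, Day 29 and Day 43 values, which is a separate question about what is being estimated.

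**What to change.** Specify the MMRM as treatment, visit, treatment-by-visit, Baseline and Baseline-by-visit, with an unstructured covariance, and take the treatment contrast at each visit from that model. State whether the third visit in the model is Day 43 or EOS, and how subjects who clear early enter it; the extra term does not settle that by itself.

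The cost is one model term (two degrees of freedom) and a sentence or two of text, with no new data or subjects. If the slopes are in fact equal, the loss is negligible: the simulated final-visit SE was 0.737 with or without the term. The change should be made before unblinding.
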